Cerebellar tDCS, gait and balance training in PwMS

PI: [name]
IRB ID #: 201912430

Project Details

I. Project Introduction

I.1 *Project to be reviewed by:*
IRB-01

I.2 *Project Title:*
The effects of 4 mA cerebellar transcranial direct current stimulation combined with gait and balance training in people with multiple sclerosis

I.3 *Short Title (optional):*
Cerebellar tDCS, gait and balance training in PwMS

I.4 *Provide a short summary of the purpose and procedures of the study proposed in this IRB application.*

- **DO NOT include information on studies not proposed in this application.**
- **Use LAY terminology only. This must be easily understandable by IRB community members and nonscientists.**
- **DO NOT cut and paste technical abstracts from funding applications that may not be understood by a general audience.**

The purpose of this study is to investigate the effects of cerebellar transcranial direct current stimulation (tDCS) combined with gait or balance training on glucose uptake in the leg muscles as well as gait and balance performance. We will conduct tDCS or SHAM followed by balance or gait training over 9 days. We will evaluate gait and balance with well-established functional tasks and changes in glucose uptake with PET-FDG imaging.

I.5 *Specify your research question(s), study aims or hypotheses (do not indicate "see protocol")*
Our research question is whether tDCS combined with gait and balance training can improve gait and balance performance as well as increase glucose uptake symmetry in the leg muscles of people with multiple sclerosis. We hypothesize that gait, balance, and glucose uptake symmetry will improve in both groups that received training (gait or balance) combined with tDCS compared to the groups that only receive training (sham tDCS). Moreover, we hypothesize that the greatest improvements will be seen in the gait and tDCS group.

I.6 *Background and significance and/or Preliminary studies related to this project. (do not indicate "see protocol")*

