Many people with multiple sclerosis (PwMS) have decreased balance (1,2) and postural control(3), gait deficits(4), and a high frequency of falls(5). High fall rates and mobility impairments pose a significant risk to the independence and quality of life of PwMS(8,9). Therefore, effective interventions to improve gait, balance and postural control are urgently needed to decrease the frequency of falls in PwMS. Gait and balance training has been demonstrated to significantly improve postural control and gait in PwMS (10,11). However, a standardized protocol for balance interventions has not been established. However, the cumulative evidence shows that only small improvements in walking ability are associated with exercise training short-term and the long-term effects are ambiguous (13). One possible treatment modality to amplify the effects of gait balance training is transcranial direct current stimulation (tDCS), a non-invasive means to increase cortical excitability and potentially prime the brain for task specific learning(14). The cerebellum plays a vital role in balance and posture and may be an important target structure for tDCS studies seeking to improve gait and balance (14-17). Studies have shown that anodal cerebellar tDCS is effective in improving balance control in older adults with high fall risk(18) and patients with chronic stroke(19). However, the most effective tDCS intensity and the duration of the effects on gait balance control has not been established(20,21).

I.7***Literature cited / references (if attaching a grant or protocol enter N/A).***

1. Martin, C. L., Phillips, B. A., Kilpatrick, T. J. et al. Gait and balance impairment in early multiple sclerosis in the absence of clinical disability. *Mult Scler* 12, 620-628, doi:10.1177/1352458506070658 (2006).
3. Cameron, M. H. & Lord, S. Postural control in multiple sclerosis: implications for fall prevention. *Curr Neurol Neurosci Rep* 10, 407-412, doi:10.1007/s11910-010-0128-0 (2010).

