GAIT TRAINING: The gait training protocol is aimed to improve walking velocity, balance, fatigability, and cognitive functions during motor dual tasks. This protocol has been used previously by Jonsdottir et al. (2018, 2020) and resulted in significant improvements in fatigability, speed, and mobility with a moderate improvement in balance measures. The treadmill training will be performed without body weight support, but subjects may hold onto handrails for balance support if necessary. The exercise intensity will be based on the participant's Rate of Perceived Exertion (RPE) on a scale from 0-10 and the training goal will be to maintain an intensity between 5-6. Therefore, treadmill speed and slope will be regulated based on relative intensity. Heart rate will also be monitored with a heart rate strap placed around the chest. The treadmill training sessions will consist of three different walking bouts: 1) Aerobic bout (minutes 0-12): preferred walking speed for the first 3 minutes, then the treadmill speed and slope will be increased as necessary to maintain the desired RPE range until the end of minute 12. RPE will be maintained between 5-6 and heart rate will not exceed 80% of age-predicted maximum heart rate. 2) Dual-task phase (minutes 13-22): preferred walking speed will be maintained while the participant completes motor dual-task activities such as changing walking motions (e.g., long steps, walking on toes, and knee lifts), head rotations, and walking with eyes closed. 3) Second aerobic phase (minutes 23-34): increase in walking speed and slope as necessary to maintain the desired RPE until the end of minute 31. RPE will be kept between 5-6 and heart rate will remain below 80% of age-predicted maximum heart rate. The last three minutes will consist of walking at their preferred speed.

BALANCE TRAINING: The balance training protocol will be based on previous work by Hebert et al. (2011) and will include a variety of both static and dynamic balance exercises on both compliant (i.e., foam and trampoline) and firm surfaces⁴⁶. Example exercises include performing head rotations and ball catching and tossing during walking and while using a variety of increasingly difficult stances (i.e., heels and toes together, half-tandem, and full tandem stance). Each training session will last approximately 40 minutes.

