A stimulation (sham vs. 4 mA) by training (balance vs. gait) by time (24 hours, 2 weeks, and 4 weeks) ANCOVA with baseline measurements as covariates will be conducted on each outcome variable (e.g., distance walked on the 6MWT and FGA score) to compare the short- and long-term effects of gait and balance training combined with ctDCS. Levene's test and normality tests (QQ plots, Shapiro Wilk test, and histograms) will be used to test the statistical assumptions. Post-hoc testing (paired and unpaired t-tests) and effect sizes (Cohen's d) will be calculated to clarify significant main or interaction effects. Significance will be accepted at $p < 0.05$ and adjusted with a Bonferroni correction. Statistical analyses will be performed using SPSS 27 (IBM Corp, Armonk, NY, USA).

XI.2*Provide the rationale or power analysis to support the number of subjects proposed to complete this study.*

We used effect sizes (Cohen's $d = 2.08$ and 1.37 , respectively) from Pilloni et al. 202060 and Hebert et al. 201146 to calculate the required sample size. With a significance fixed at $p = 0.05$ and 80% power, we will require 40 total subjects ($n = 10$ in each group) to properly power the hypothesis test for a statistically significant change. Based on this calculation and the assumption of a standard drop out rate of approximately 20%, we propose to recruit 48 total subjects ($n = 12$ in each group).

XII. Future Research

XII.1 *Do you wish to keep any information about subjects involved with this research project so that members of the current research team may contact them in the future for your own research projects?*
Yes

XII.2 *Do you wish to keep any information about subjects involved with this research project so that other researchers may contact them for future research?*
Yes

XII.3 *List the data or information you will keep:*
Contact information and outcome of the phone questionnaire.

XII.4 *Does this project involve storing any data, tissues or specimens for future research?*
Yes – contribution for future use is mandatory for participation in the study

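### The 80% power in XI.2 is not established for the tDCS-versus-sham hypothesis: 10 per group follows from an effect size taken from the source of the balance training, which active and sham arms both receive

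*Combined protocol and SAP*

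**What the plan says.** - **Power (XI.2).** Two effect sizes are cited from two studies, d = 2.08 and d = 1.37. "With a significance fixed at $p = 0.05$ and 80% power", the plan arrives at 40 subjects, 10 in each of four groups, said to be sufficient "to properly power the hypothesis test for a statistically significant change". Recruitment is set at 48. The section names no outcome, time point, contrast or test, and does not say which d was used.
- **Hypothesis (I.5).** The stated expectation for the walking, balance and PET outcomes is that they "will improve in both groups that received training (gait or balance) combined with tDCS compared to the groups that only receive training (sham tDCS"). The greatest gain is expected with gait training plus tDCS.
- **Arms (VII.E.2 and VII.E.6).** A two-by-two layout: 4 mA or sham stimulation, each with balance or gait training.
- **Balance training (VII.E.6).** It is based on a 2011 study and "will include a variety of both static and dynamic balance exercises". XI.2 names the same study, under the same reference number, as the source of d = 1.37. The list in I.7 contains a 2011 study by the same first author, whose title describes a randomized trial of vestibular rehabilitation.
- **Analysis (XI.1).** A stimulation by training by time ANCOVA with baseline as covariate. "Significance will be accepted at $p < 0.05$ and adjusted with a Bonferroni correction". The number of comparisons is not given.

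**The concern.** The I.5 hypothesis is about what tDCS adds to training. Within the balance pair, both arms get the same training, and so do both arms of the gait pair. An effect size that measures what training achieves says nothing about the difference between two arms that share it. If the sample size was set by such a value, the 80% belongs to a different question.

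The consequence lies in interpretation. A non-significant stimulation effect from a trial described as properly powered would be read as evidence against adding tDCS, although the plan has not shown which add-on effects it could detect.

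**Working it through.** **Inputs.** From XI.2: alpha 0.05, power 80%, d = 2.08 and 1.37, 10 per group. From XI.1: baseline-adjusted ANCOVA and Bonferroni correction. Assumed here, because the plan does not state them: two-sided testing, two comparisons for Bonferroni, and a baseline-to-follow-up correlation r of 0.5 to 0.7.

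**Step 1: reproduce the plan's figure.** For a two-sample t-test with n per group, the noncentrality is d × √(n/2) on 2(n − 1) degrees of freedom.

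| d | n per group for 80% | Rounded | Total | Power at 10 v 10 |
|---|---|---|---|---|
| 1.37 | 9.43 | 10 | 4 × 10 = 40 | 82.6% |
| 2.08 | 4.81 | 5 | 4 × 5 = 20 | 99.3% |

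At d = 1.37 and n = 10 the noncentrality is 1.37 × √5 = 3.06 on 18 degrees of freedom. With 9 per group, power is 77.9%, so 10 is the smallest n that reaches 80%.

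Other routes do not give 10 per group:
- one-sided t-test at d = 1.37: 8 per group
- normal approximation at d = 1.37: 9 per group
- mean of the two values, d = 1.725: 7 per group
- paired t-test: 7 (d = 1.37) or 5 (d = 2.08)
- four-cell ANOVA with f = d/2 at d = 1.37: 20 or 28 in total (1 or 3 numerator degrees of freedom)

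**Step 2: trace d = 1.37.** XI.2 and the balance training paragraph in VII.E.6 cite the same study under number 46. The I.7 list carries a study matching by first author and year as item 10, so the title is linked on that basis, not by number. The title concerns rehabilitation and does not mention stimulation.

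**Step 3: add the planned correction.** With two comparisons, alpha is 0.05/2 = 0.025. Power at d = 1.37 and 10 v 10 falls from 82.6% to 72.8%.

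**Step 4: detectable tDCS-versus-sham differences.** These are for 80% power, two-sided, with 10 completers per group. Baseline adjustment multiplies the detectable d by √(1 − r²), which is 0.866 at r = 0.5 and 0.714 at r = 0.7.

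| Contrast | Alpha | No baseline adjustment | r = 0.5 | r = 0.7 |
|---|---|---|---|---|
| Within one training type, 10 v 10 | 0.05 | 1.32 | 1.15 | 0.95 |
| Pooled over training, 20 v 20 | 0.05 | 0.91 | 0.79 | 0.65 |
| Within one training type, 10 v 10 | 0.025 | 1.48 | 1.29 | 1.06 |
| Pooled over training, 20 v 20 | 0.025 | 1.01 | 0.87 | 0.72 |

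The adjusted figures are approximate: they ignore the degree of freedom spent on the covariate and any gain from repeated follow-up measurements.

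**The case against.** The strongest reply is that two effect sizes are cited and the contrast behind neither is shown. The d = 2.08 source is not described in the text available. If it measured tDCS against sham, 10 v 10 would give about 99% power for it, and sizing on the smaller value would look cautious. Likewise, the outcome and comparison behind d = 1.37 are not stated, and its role in setting the sample size is inferred from arithmetic. All of this stands. It limits the conclusion to *not established*. It does not rescue the 80%, because nothing in XI.2 makes the link to the I.5 contrast.

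Three stronger readings are tempting, and the documents do not support them.

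- **That the trial is shown to be underpowered, or can detect only very large effects.** The planned ANCOVA adjusts for baseline, and the pooled stimulation effect uses 20 v 20. At an assumed d of 0.8, its power at alpha 0.05 is 69% without baseline adjustment and 81% to 93% with r of 0.5 to 0.7. Bonferroni pulls the other way by an amount the plan leaves open.
- **That the background predicts a small effect.** I.6 does say that "only small improvements in walking ability are associated with exercise training short-term", but that concerns exercise, not the increment from tDCS.
- **That the pooled stimulation effect must become the primary contrast.** I.5 hypothesises benefit in both training types and the greatest gain with gait plus tDCS. Reducing the within-training contrasts to estimation would change those hypotheses. That is a trade-off for the investigators, not a correction of an error.

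**Conclusion.** The point holds in a limited form. The sample size of 40 is reproduced exactly by d = 1.37 and by no other reading tried. The documents tie that value to the source of a training programme common to an active and a sham arm. For the gait pair, it is not even the source of the training used. The claim that 40 subjects properly power the hypothesis test is therefore unsupported for tDCS versus sham. It also omits the Bonferroni correction, which with two comparisons would cost about 10 percentage points at the plan's own d (83% to 73%).

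This rests on a two-sided two-sample t-test for the reproduction, on the match by author and year between XI.2 and I.7, and on assumed values for the number of comparisons and the baseline correlation. Whether the true power is adequate cannot be settled from the documents, because they identify no effect size as tDCS versus sham.

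**What to change.** Revise XI.2 as follows.

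1. Remove the statement that 40 subjects properly power the hypothesis test, unless a tDCS-versus-sham effect size is given and justified, with its source, outcome and contrast.
2. Name the outcome, time point and contrast to which the power statement applies.
3. State the number of comparisons covered by the Bonferroni correction and use the adjusted alpha.
4. Give detectable tDCS-versus-sham differences under the planned baseline-adjusted ANCOVA, within training type and pooled, with the assumed baseline correlation. The table above is a guide, not text to copy: its alpha and correlation are assumptions.
5. State that a non-significant result will be read against those detectable differences.

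This needs no extra patients, visits or procedures, and leaves the hypotheses and the analysis model as they are. The cost is a power statement that is likely to look less favourable.

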V.26 *The study involves Department of Nursing Services and Patient Care nursing, nursing resources or evaluates nursing practices at UI Health Care.*
 No

VI. Subjects

VI.1 *How many adult subjects do you expect to consent or enroll for this project?*
 48

VI.2 *What is the age of the youngest adult subject?*
 18.0

VI.3 *What is the age of the oldest adult subject?*
 75.0

VI.4 *What is the percentage of adult male subjects?*
 30

VI.5 *What is the percentage of adult female subjects?*
 70

VI.6 *How many minor subjects do you expect to consent or enroll for this project?*
 0

VI.13 *Describe EACH of your subject populations*

- *Include description of any control group(s)*
- *Specify the Inclusion/Exclusion criteria for EACH group*

Inclusion criteria: medically diagnosed with relapsing-remitting multiple sclerosis, 18-75 years of age, moderate disability (score of 2-6 on the Patient Determined Disease Scale [PPDS]), self-reported differences in function between legs, able to walk on a treadmill for at least 20 mins, and not taking any psychoactive medication.

Exclusion criteria: relapse within the last 60 days, have changed disease modifying medications in the last 45 days, are currently pregnant, have a concurrent neurological or neuromuscular disease, have been hospitalized within the last 90

days, have any contraindications for the tDCS device (i.e., pacemakers or metal implants), or are unable to understand/sign the consent form.

VI.14 *Provide an estimate of the total number of subjects that would be eligible for inclusion in each of your study populations (include your control population if applicable)*
48

VI.15 *Describe how you will have access to each of your study populations in sufficient number to meet your recruitment goals.*
We will generate a list of MS patients from our population seen in the Neurology clinic whose diagnosis is listed as MS in Epic. Furthermore, we will distribute flyers around the UIowa clinics and hospital.

VI.16 *Do you plan to recruit/enroll non-English speaking people?*
No

VI.18 *Do you propose to enroll any of the following in this study as subjects?*

- *Employee of the PI or employee of a research team member*
- *Individual supervised by PI or supervised by member of research team*
- *Individual subordinate to the PI or subordinate to any member of the research team*
- *Student or trainee under the direction of the PI or under the direction of a member of the research team*

No

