- *Procedures include a confederate pretending to be another participant in the study.*
- *Participants will be told that the research includes completion of a particular task, when in fact, that task will not be administered.*
- *Study is designed to introduce a new procedure (or task) that participants are not initially told about.*
- *If yes, a waiver of informed consent must be requested under question IV.3.*

No

VII.E. Project Description (E)

VII.E.1 *Will subjects be randomized?*
 Yes

VII.E.1.a *Will any subjects be blinded to which study arm they have been assigned?*
 Yes

VII.E.1.b *Does the protocol permit telling subjects their treatment assignment at the end of the entire study?*
 Yes

VII.E.1.c *Describe the circumstances under which subjects will be told what study arm they have been assigned.*
 At the end of all sessions the participant will be informed about the study arm in which they were involved.

VII.E.2 *Describe randomization scheme/assignment including ratio such as 1:1, 2:1 etc.*
 The study will be a double-blind and sham-controlled. Forty participants will be randomly assigned into four groups (Sham and balance training, 4 mA tDCS and balance training, sham and gait training, and 4 mA and gait training). Participants will undergo 9 sessions of tDCS combined with either gait or balance training.

VII.E.3 *Will any questionnaires, surveys, or written assessments be used to obtain data directly from subjects in this study?*
 Yes

VII.E.4 *List all questionnaires, surveys, written assessments and ATTACH each one to the application. (NOTE: You are NOT prohibited from attaching copyrighted materials to this application)*
 Patient Determined Disease Steps (PDDS)
 Fatigue Severity Scale (FSS)

VII.E.5 *Does this project involve creating any audiotapes, videotapes, or photographs?*
 No

VII.E.6 *Provide a detailed description in sequential order of the study procedures following the consent process - DO NOT cut and paste from the Consent Document.*

Describe study populations separately if they will be participating in different procedures - include CONTROL population if applicable.

DESCRIBE:

- *What subjects will be asked to do/what happens in the study (in sequential order)*
- *The time period over which procedures will occur*
- *The time commitment for the subject for individual visits/procedures*

- **Long-term followup and how it occurs**

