PwMS will be randomly assigned to one of four groups: ctDCS and gait training, sham and gait training, ctDCS and balance training, or sham and balance training (n = 12 per group). Each subject will attend a total of 14 experimental sessions. Session 1 will be a familiarization session and will last approximately 45 minutes. The duration of the baseline (Session 2) and 24-hour post-intervention session (Session 12) will be approximately 3 hours. The ctDCS and gait training sessions (Sessions 3 – 11) will last approximately 1.5 hours. Finally, the two- and four-week post-intervention sessions (Sessions 13 and 14, respectively) will be approximately one hour. During the initial session, subjects will be consented and complete strength testing to objectively determine the more-affected leg. Additionally, during Session 1 subjects will become familiar with treadmill walking and determine a self-selected speed for subsequent testing sessions. During the baseline session (Session 2), subjects will 1) complete the Fatigue Severity Scale (FSS)63, 2) undergo a whole-body FDG/PET scan after 20 minutes of treadmill walking at their self-selected speed, 3) perform the Functional Gait Assessment (FGA), 4) Timed 25-Foot Walk Test (T25WT), 5) Berg Balance Scale (BBS), 6) static posturography, and 7) the 6-minute walk test (6MWT) while wearing inertial sensors. The following 9 days will include 20 minutes of either 4 mA or sham ctDCS, 10 minutes of rest to allow for peak stimulation effects, and then approximately 40 minutes of gait or balance training. Session 12 will consist of the same testing battery as Session 2. Long term effects (2- and 4-weeks post-intervention) will be assessed with the 1) FSS questionnaire, 2) FGA, 3) T25FW, 4) BBS, 5) static posturography, and 6) the 6MWT during Sessions 13 and 14.

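### The number to be randomised is forty in VII.E.2 but 12 per group (48) in VII.E.6; separately, and of minor consequence, 48 recruits leave about 38 completers at XI.2's 20% dropout, not 40

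*Combined protocol and SAP*

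**What the plan says.** The combined protocol and SAP gives the sample size in four places.

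- **VII.E.2 (randomisation scheme):** "Forty participants will be randomly assigned into four groups". No allocation ratio is given.
- **VII.E.6 (study procedures):** random assignment to the same four groups, the last listed as "sham and balance training (n = 12 per group". Four groups of 12 make 48; the total is implied, not written.
- **VI.1:** the form asks "How many adult subjects do you expect to consent or enroll for this project", and the answer is 48.
- **XI.2 (power):** "With a significance fixed at $p = 0.05$ and 80% power, we will require 40 total subjects ($n = 10$ in each group", which is said "to properly power the hypothesis test for a statistically significant change". The inputs are Cohen's d of 2.08 and 1.37 from two cited studies. XI.2 then allows for dropout: "the assumption of a standard drop out rate of approximately 20%, we propose to recruit 48 total subjects", with 12 in each group.

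XI.2 names no outcome, test or sidedness. XI.1 describes the analysis as "A stimulation (sham vs. 4 mA) by training (balance vs. gait) by time (24 hours, 2 weeks, and 4 weeks) ANCOVA", with baseline as covariate. Significant effects are followed by paired and unpaired t-tests, and significance at 0.05 is Bonferroni-adjusted.

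**The concern.** The number randomised fixes the allocation list and the power, and the two sections that describe random assignment give different values. VII.E.2 is where a person building the list would look, and its figure equals XI.2's requirement before dropout. Followed literally, it leaves no allowance for dropout. VII.E.7 says that participants lost to follow-up will not be recontacted, so losses would not be made up that way.

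XI.2 has a smaller fault of its own: the allowance for dropout does not return the 40 completers that the section says it needs. Because XI.2 names no comparison, a reader also cannot tell which of the tests planned in XI.1 the 80% describes.

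**Working it through.** **Inputs.** From XI.2: d = 1.37 and 2.08, alpha 0.05, power 80%, 40 required, 48 recruited, about 20% dropout. From VII.E.2: 40 randomised. From VII.E.6: 12 per group. Assumptions: two-sided test, equal groups, and (step 5 only) a correlation rho between baseline and outcome, which the documents do not give.

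**1. Reproducing the 40.** For a two-group t-test with n per group, the noncentrality is d x sqrt(n/2) with 2n - 2 degrees of freedom (df).
- d = 1.37, n = 10: noncentrality 3.06, df 18, power 0.826.
- d = 1.37, n = 9: power 0.779.
- d = 2.08: 5 per group is enough (power 0.82).

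So 10 is the smallest group size that gives 80% at the smaller effect, and 4 x 10 = 40. The figure reproduces as an unadjusted two-sided comparison of one group with another.

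**2. Reproducing the 48.** 40 x 1.2 = 48. Dividing by the retention rate gives 40 / (1 - 0.20) = 50.

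**3. If 48 are randomised.**
- Completers at 20% dropout: 48 x 0.80 = 38.4, or 9.6 per group.
- Power at 9.6 per group, d = 1.37: 0.808.
- Dropout at which 40 complete: 1 - 40/48 = 16.7%.

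**4. If 40 are randomised.**
- Completers at 20% dropout: 40 x 0.80 = 32, or 8 per group.
- Group versus group, d = 1.37: noncentrality 2.74, df 14, power 0.722.
- Pooled tDCS versus sham, 16 against 16, d = 1.37: noncentrality 1.37 x sqrt(8) = 3.87, df 30, power 0.963.

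**5. What the 80% covers, at exactly 10 per group and an effect of 1.37 SD.** With baseline as covariate in the four-group model at one time point, the standard error is multiplied by sqrt(1 - rho^2) and df = 35. Before that factor it is sqrt(2/10) SD for a group contrast and sqrt(4/10) SD for the stimulation x training interaction.

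| Comparison | Power |
|---|---|
| Group versus group t-test, alpha 0.05 | 0.83 |
| Same, alpha 0.025 (Bonferroni for two tests) | 0.73 |
| Pooled 20 versus 20 t-test, alpha 0.05 | 0.99 |
| Interaction, baseline-adjusted, rho 0 / 0.3 / 0.5 / 0.7 | 0.56 / 0.60 / 0.68 / 0.84 |
| Group contrast, baseline-adjusted, rho 0 / 0.3 / 0.5 / 0.7 | 0.85 / 0.88 / 0.93 / 0.99 |

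The interaction reaches 80% at rho of about 0.66.

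**The case against.** **The two figures might describe different stages: 48 recruited, 40 randomised.** VI.1 and XI.2 do speak of enrolling and recruiting, so neither strictly states a number randomised. That stands: the direct contradiction is VII.E.2 against VII.E.6. The two-stage reading still fails, because VII.E.6 places 12 per group at random assignment, and VII.D.25 plans no eligibility screening after consent that would reduce 48 to 40.

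**The dropout shortfall has almost no effect.** This stands. The rate is only approximate, and 40 is itself rounded up: 80% power at d = 1.37 needs about 9.43 per group, and 48 recruits leave 9.6. A reader might infer that the trial must enrol 50, or 52 in equal groups (10 / 0.80 = 12.5, rounded up to 13). The power figures do not call for it.

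**A reader might infer that the trial is underpowered.** The documents do not support this in general. I1.5's first hypothesis compares tDCS with sham, and pooled over training that effect has power of about 0.96 even with 32 completers. The 0.72 applies only to an unadjusted comparison of two single groups.

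**A reader might infer that the interaction is underpowered.** An interaction of 1.37 SD is an illustration, not a figure from the plan. The 0.56 ignores any gain from the planned baseline covariate; the answer depends on a correlation that the documents do not give. The hypothesis that gait training with tDCS does best could also arise from two additive main effects.

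**A reader might infer that the post-hoc tests are wrong.** XI.1 never says that its t-tests are unadjusted. That is a plausible reading, not a demonstrated error.

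**Conclusion.** The conflict between forty in VII.E.2 and 12 per group in VII.E.6 is real and should be reconciled. That VII.E.2 carried over the pre-dropout figure is likely but an inference. The consequence is conditional: power falls to about 0.72 for a single group comparison only if 40 are actually randomised and 20% drop out.

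The dropout arithmetic in XI.2 is inexact but minor, at about 0.81 with 48 recruited. The required 40 is not shown to be wrong. It is consistent with one particular test, but XI.2 does not say that this test was used. If it was, the 80% does not carry over to Bonferroni-adjusted group t-tests at the same effect, nor to an interaction of 1.37 SD unless baseline correlation is about 0.66 or more.

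All power figures assume d = 1.37, two-sided testing and equal groups; those for the baseline-adjusted model also assume a single time point.

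**What to change.** 1. **One number randomised.** Reconcile forty in VII.E.2 with the 48 in VII.E.6, VI.1 and XI.2, so that the same figure appears throughout.
2. **Dropout statement in XI.2.** Say that 48 recruits give about 38 completers at 20% dropout, or 40 completers at 16.7%. No added enrolment is needed.
3. **Scope of the 80% in XI.2.** Name the comparison, outcome and sidedness that it refers to. If it is the unadjusted two-sided comparison of two groups at d = 1.37, say that it does not extend to Bonferroni-adjusted group t-tests, and that for an interaction of that size it depends on the baseline correlation.
4. **Optional, in XI.1.** State that post-hoc between-group contrasts are taken from the planned baseline-adjusted four-group ANCOVA and not from separate unadjusted t-tests. Over the assumed correlations 0 to 0.7, power would be 0.85 to 0.99 against 0.83.

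The cost is wording in VII.E.2, XI.1 and XI.2, with no added participants, visits or data. The contrasts in item 4 come from the model already planned. The price is a narrower power claim.
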